### **9.4. General statistical Methods**

#### **9.4.1. Demographics and Baseline Characteristics**

Demographic and baseline characteristics will be listed by study site and patient, and will be summarized by treatment. Frequencies and proportions will be presented for the categorical variables and descriptive statistics will be presented for continuous variables.

#### **9.4.2. Exposure**

Treatment exposure will be listed by study site and patient, and will be summarized by doses administered, as well as total exposure to FX006. Time between FX006 exposure (1st and 2nd doses) will be summarized.

#### **9.4.3. Exploratory Efficacy Analyses**

The examination of efficacy is exploratory in this study. Data from the WOMAC® questionnaire will be presented in by-patient listings with summary presentation of the data and exploratory analyses.

Analysis of the magnitude of pain relief observed with WOMAC A (pain), stiffness (WOMAC B), and function (WOMAC C) will be explored between patients who receive one or two doses of FX006 will be explored with longitudinal mixed model for repeated measures (MMRM) with fixed effects of number of doses (1 or 2) received, and a dose by time interaction. Model covariates will include study site, and potentially other variables. Subject will be a random effect in the model. The exact configuration for the MMRM will be fully described in the SAP or interim analysis plans.

A within subject analysis will be completed to examine the differences in WOMAC scores following the first dose, and then following a second dose of FX006. Change from baseline for the first dose and change from last assessment prior to second dose will be completed with linear models. The details of the linear model will be specified in the SAPEvaluation of dose-response

will be assessed descriptively with an examination of WOMAC A responses at the time (in weeks) of second dose administration to assess the magnitude of scores at each week that a second dose may be administered. The time to maximal pain relief response with WOMAC A (pain) following the first and second doses of FX006 will be examined using a Kaplan-Meier (KM) procedure.

Questionnaire data from the GPAQ domains (occupational physical activity, transport-related physical activity, and physical activity during discretionary or leisure time) will be described descriptively at the two time points collected (Screening and Week 12). The change in GPAQ domain scores and total score will be examined with an analysis of variance (ANOVA) model with summaries comparing patients who receive one dose to those receiving two doses of FX006. GPAQ information collected at Screening will be utilized to normalize steps per day based on lifestyles activity. GPAQ information will be a model covariate in subsequent analyses.

#### **9.4.4. Safety Analyses**

AEs will be coded using the Medical Dictionary for Regulatory Activities (MedDRA) dictionary. Incidences (number and percent) TEAEs, those events that started after dosing or worsened in severity after dosing, will be presented by treatment group. Incidences of TEAEs will also be presented by maximum severity and relationship to study medication. Similar presentations will be provided for serious AEs, AEs leading to withdrawal from the study, or AEs leading to death.

Analysis of AE data will include examination of the incidence rates and changes in severity of TEAEs and index knee related TEAEs following the first dose and second dose, as well as the cumulative incidence of TEAEs after all doses of FX006. Both the number of events and the number of patients experiencing an event will be examined to assess the by patient cumulative incidence of TEAEs associated with repeat administration. The cumulative TEAE incidence rate will also be compared with total exposure to FX006.

Clinical laboratory data and vital sign information will be presented as descriptive summary statistics for value and change from Baseline at each individual time point.

## 10. DATA QUALITY ASSURANCE

At the time the study is initiated, the clinical study monitor will thoroughly review the final protocol and the eCRF with the Principal Investigator and staff. During the course of the study, the clinical study monitor will visit the clinical site regularly to check the completeness of the patient records, the accuracy of entries into the eCRF, the adherence to the final protocol and to International Conference on Harmonisation GCP, the progress of enrollment, and the storage, dispensing and accountability of study medication. The Principal Investigator and key study personnel should be available to assist the clinical study monitor during these visits.

The Principal Investigator will give the monitor, auditor(s), Sponsor, Sponsor designee and regulatory authorities direct access to relevant clinical records to confirm their consistency with the eCRF entries. No information in these records about the identity of the patients will leave the clinical site. The Sponsor will maintain the confidentiality of all patient records.

Source data is all information in original records and certified copies of original records of clinical findings, observations, or other activities in a clinical trial necessary for the reconstruction and evaluation of the trial. Source data are contained in source documents (original records or certified copies).

Independent clinical quality assurance audits may be performed at any time during or following completion of the Study by the Sponsor, or its authorized agents, and Competent Authorities and/or the IRB/EC.

## 11. DATA HANDLING AND RECORDKEEPING

### 11.1. Case Report Forms

The eCRF will be supplied by the Sponsor or designee and should be handled in accordance with the instructions provided. All study data should initially be documented in source documents (e.g., patient charts, notes, laboratory reports, ECG recordings, etc.) and then subsequently entered from the source into the eCRF. All eCRFs should be filled out completely by examining personnel or the study coordinator. The eCRF is reviewed, signed, and dated electronically by the Principal Investigator.

### 11.2. Study Medication Accountability

All study medication required for completion of this study will be provided by the Sponsor or designee. Study medication will be acknowledged upon receipt indicating shipment content and condition. Damaged supplies will be replaced.

Accurate records of all study medications received by, dispensed from, or returned by the study site should be maintained within the Drug Tracking Module.

In the event of a temperature excursion, refer to the Pharmacy Binder for instructions. In the event of a product complaint, complete the Product Complaint Form located in the Pharmacy Binder and send to [[contact]](mailto:[contact]). The assigned monitor or clinical manager will coordinate with the Sponsor for further guidance.

### 11.3. Confidentiality of Data

Patient medical information obtained by this study is confidential, and disclosure to third parties other than those noted below is prohibited.

Upon the patient's permission, medical information may be given to his or her personal physician or other appropriate medical personnel responsible for his or her welfare.

Data generated by this study must be available for inspection by representatives of Competent Authorities, the Sponsor or their representative, and the IRB/EC.

To maintain patient privacy, all eCRFs, study drug accountability records, study reports, and communications will identify the patient by initials where permitted and/or by the assigned patient number. The patient's confidentiality will be maintained and will not be made publicly available to the extent permitted by the applicable laws and regulations.

### 11.4. Retention of Records

In accordance with US federal regulations (21 CFR 312.62[c]), the Sponsor requires that records and documents pertaining to the conduct of this study and the distribution of study medications, including eCRFs, consent forms, laboratory test results, glucose source data, and medical inventory records, must be retained by the Principal Investigator for 2 years after marketing application approval. If no application is filed, these records must be kept 2 years after the investigation is discontinued and the regulatory authorities are notified. The Sponsor or their

representative will notify the Principal Investigator of these events. In the event that local regulations are more stringent than that specified above, the local regulations will be adhered to. If local records retention regulations are more stringent than that specified above, the local regulations will prevail.

### **11.5. Protocol Adherence**

The Principal Investigator must adhere to the protocol as detailed in this document and agrees that any changes to the protocol must be approved by the Sponsor or their representative prior to seeking approval from the IRB/EC. When the changes involved are only logistical and administrative in nature to trial this may not require prior approval by the IRB/EC. The Principal Investigator will be responsible for enrolling only those patients who have met protocol eligibility criteria.

## 12. PUBLICATION POLICY

### 12.1. Sponsor's Publication Policy

Sponsor or its designee shall have the right to publish or otherwise publicly disclose the information contained in or related to the Study Drug, the Study Data, or other Confidential Information in any form without the written consent of Site, the Principal Investigator or any other person. Each of Site and Principal Investigator further agrees that Sponsor shall have the exclusive right to commercialize any products or services that are based upon, or derived from the Study Drug, the Study Data, or other Confidential Information.

### 12.2. Site Publication

After the Study is completed, which means that all completed eCRFs have been received by Sponsor, and the database has been locked at all participating sites and Study closeout visits have taken place at all participating sites, then Site shall have the right, subject to the HIPAA Rules, to publish or otherwise make public data resulting from the conduct of the Study at the Site upon the earlier of (a) the date of publication of a multi-center publication coordinated by Sponsor with respect to the data resulting from the Study, and (b) the date of submission of the data resulting from the Study by Sponsor to the FDA for regulatory approval; provided that Site shall furnish Sponsor with a copy of any proposed publication or release at least 90 days in advance of the proposed submission or presentation date. Within this 90-day period, the Sponsor shall review such proposed publication or release to determine whether it contains any Confidential Information (other than Study Data), or whether Sponsor desires to file patent applications on subject matter contained therein, and to ensure the accuracy of the information contained in the publication or release. Upon receiving any notification from Sponsor requesting deletion of Confidential Information (other than Study Data), requesting correction of inaccuracies, or requesting a delay in publication of up to 90 days to allow the filing of patent applications before publication or release, Site shall take the requested action. The parties acknowledge and agree that Site shall be solely responsible for the editorial content of any such publication or release. In a manner consistent with customary practice, Site shall acknowledge the support and contributions of Sponsor, if requested by Sponsor, in connection with the Study, in any and all publications and presentations reporting and data resulting from the Study. Site and the Principal Investigator shall comply with all applicable federal and state laws and other applicable rules and requirements regarding disclosure of industry support (financial or otherwise) in connection with such publications and presentations.

## 14. APPENDICES

### APPENDIX 1. KNEE OA DIAGNOSIS ASSESSMENTS

#### American College of Rheumatology Criteria for Classification of Idiopathic OA of the Knee (Altman et al, 1986)

##### **Clinical and radiological**

- Knee Pain
- + at least 1 of 3:
  - Age > 50 years
  - Stiffness < 30 minutes
  - Crepitus
- + Osteophytes

#### Kellgren-Lawrence Grade of Knee X-ray

- Grade 0: no findings
- Grade 1: doubtful narrowing of joint space and possible osteophytic lipping
- Grade 2: definite osteophytes and possible narrowing of joint space
- Grade 3: moderate multiple osteophytes, definite narrowing of joint space and some sclerosis and possible deformity of bone ends
- Grade 4: large osteophytes, marked narrowing of joint space, severe sclerosis and definite deformity of bone ends

## APPENDIX 2. STUDY VISIT FLOW CHART

## ABBREVIATIONS

Abbreviation	Definition
ACR	American College of Rheumatology
AE	Adverse Event
ANCOVA	Analysis of Covariance
AUE	Area Under the Effect Curve
BMI	Body Mass Index
BP	Biomarker Population
CI	Confidence Interval
CM	Concomitant Medication
CRF	Case Report Form
CSR	Clinical Study Report
CTCAE	Common Terminology Criteria for Adverse Events
ECG	Electrocardiogram
EULAR	European League against Rheumatism
FAS	Full Analysis Set
GPAQ	Global Physical Activity Questionnaire
HIV	Human Immunodeficiency Virus
IA	Intra-articular
ICH	International Conference on Harmonisation
iSAP	Interim Statistical Analysis Plan
JSN	Joint Space Narrowing
K-L	Kellgren-Lawrence
KOOS	Knee injury and Osteoarthritis Outcome Score
LSM	Least Square Means
MedDRA	Medical Dictionary for Regulatory Activities
MET	Metabolic Equivalent
mg	milligram
mmol	millimole
MMRM	Mixed Effects Model for Repeat Measures
OA	Osteoarthritis
OARSI	Osteoarthritis Research Society International
PDF	Portable Document Format
PPIP	Per Protocol Imaging Population
PT	Preferred Term
QOL	Quality of Life
SAE	Serious Adverse Event
SAP	Statistical Analysis Plan
SAS®	Statistical Analysis System

Abbreviation	Definition
SBC	Subchondral Bone Changes
SD	Standard Deviation
SE	Standard Error
SI	International System of Units
SOC	System Organ Class
SP	Safety Population
TA	Triamcinolone Acetonide
TAcS	Triamcinolone Acetonide Injectable Suspension, Immediate-Release (Commercially Available)
TEAE	Treatment Emergent AE
US	United States
WHO	World Health Organization
WOMAC	Western Ontario and McMaster Universities

## 1. INTRODUCTION AND OBJECTIVES OF ANALYSIS

### 1.1. Introduction

Osteoarthritis (OA) is a painful and debilitating musculoskeletal disease that is characterized by intra-articular (IA) inflammation, deterioration of articular cartilage, and degenerative changes to peri-articular and subchondral bone (Creamer and Hochberg, 1997; Goldring and Goldring, 2006). Arthritis is the most common cause of disability in the United States (US) and OA is the most common joint disease, affecting 27 million Americans, with numbers expected to grow as a result of aging, obesity and sports injuries. Recent data suggest that OA accounts for over \$185 billion of annual healthcare expenditures in the US, which does not include loss of productivity costs. We estimate that by 2030, 45 million people will have OA. OA commonly affects large weight-bearing joints like the knees and hips, but also occurs in the shoulders, hands, feet and spine. Patients with OA suffer from joint pain, tenderness, stiffness and limited movement. As the disease progresses, it becomes increasingly painful and debilitating, culminating, in many cases, in the need for total joint arthroplasty.

Current Guidelines from the American College of Rheumatology (ACR), Osteoarthritis Research Society International (OARSI) and the European League against Rheumatism (EULAR) recommend the use of IA corticosteroids for short-term acute pain relief (ACR Subcommittee 2000; Hochberg et al, 2012; Jordan et al, 2003).

While historically OA has been considered a non-inflammatory disease, it is increasingly being recognized that chronic synovitis occurs in all stages of knee OA (Benito et al, 2005; Sellam and Berenbaum, 2010; Wenham and Conaghan, 2010). As synovial inflammation is correlated with clinical symptoms and joint degeneration, it should be an important target for therapeutic intervention. The inflamed synovium may well be the target for IA corticosteroids which are widely used in knee OA (Ayral et al, 2005).

FX006 is an extended-release formulation of triamcinolone acetonide (TA) for IA administration that is being developed for the treatment of patients with pain attributed to OA of the knee. FX006 is intended to deliver TA to the synovial and peri-synovial tissues for a period of approximately 3 months depending on the dose administered (Bodick et al, 2013).

Available clinical and nonclinical data indicate that FX006 is likely to be safe and well tolerated and has the potential to provide pain relief that is meaningfully better and more persistent than that provided by immediate release triamcinolone acetonide (TAc).

### 1.2. Objectives of Statistical Analysis

#### 1.2.1. Primary Objective

The primary objective of this study is to assess the overall safety and general tolerability of repeat administration of FX006 (two doses of 32 mg FX006) in patients with symptomatic OA of the knee.

#### 1.2.2. Exploratory Objectives

Exploratory objectives of this study include the following:

- examine efficacy signals for sustained pain reduction following two doses of 32 mg FX006.
- collect synovial fluid samples to enable potential future examination of synovial fluid biomarkers that may contribute to the pathogenesis of OA and/or be associated with responsiveness to FX006 treatment.

This statistical analysis plan (SAP) is designed to outline the methods to be used in the analysis of study data in order to answer the study objective(s). Populations for analysis, data handling rules, statistical methods, and formats for data presentation are provided. The statistical analyses and summary tabulations described in this SAP will provide the basis for the results sections of the clinical study report (CSR) for this trial.

This SAP also will outline any differences in the currently planned analytical objectives relative to those planned in the study protocol.

This SAP may be amended as study data are reviewed and interim analyses of these data are conducted.

## **2. STUDY DESIGN**

### **2.1. Synopsis of Study Design**

This study is an open-label, repeat administration design of 32 mg FX006. The study will be conducted in male and female patients  $\geq$  40 years of age with symptomatic OA of the knee.

Eligible patients will be offered participation to receive an initial IA injection of FX006 administered to the index knee at Day 1.

Patients who receive an initial injection of FX006 will return at Weeks 4 and 8 before being evaluated at 12, 16, 20 and 24 weeks following the initial administration of FX006 for repeat administration. At the first visit where the patient has been determined to meet repeat administration eligibility criteria, the patient will be eligible to receive a second IA injection of FX006 administered to the index knee.

Patients who are eligible to receive a second injection will be evaluated for a total of 52 weeks post initial injection at: Weeks 4, 8, 12, 16, 20, 24, 28, 32, 36, 40, 44, 48 and 52, regardless of the visit at which they receive their second injection.

Patients that do not benefit from the initial treatment as determined by evaluation at Week 12 will complete the study at the Week 12 follow-up visit. These patients will be evaluated for a total of 12 weeks post initial injection at: Weeks 4, 8, 12.

Patients who are not eligible for a second injection of FX006 after evaluation at Weeks 12, 16, 20, and 24 will complete the study at the Week 24 follow-up visit. These patients will be evaluated for a total of 24 weeks post initial injection at: Weeks 4, 8, 12, 16, 20 and 24.

Refer to [Appendix B](#) for the study flow chart.

### **2.2. Randomization Methodology**

No randomization technique is required to assign patients to treatment in this study.

### **2.3. Unblinding**

Not applicable to the current study since this is an open-label study.

### **2.4. Study Procedures**

The schedule of assessments, as outlined in the study protocol, is provided in [Table 1](#).

**Table 1 Schedule of Assessments**

Procedures	Screen	Baseline Day 1	Week 4	Week 8	Week 12, 16, 20, 24	Week 28, 32, 36, 40, 44, 48	Week 52/End of Study
Informed consent, OA Medical History, HIV, Hepatitis B/C, Serum Pregnancy Test, 12-Lead ECG, Height	X						
Inclusion/Exclusion Review, Medical History/Update, Prior Treatment & Medications	X	X					
Physical Examination, Hematology & Chemistry	X				X		X
Index Knee X-ray, Weight and BMI	X						X
Index Knee Assessment, Vital Signs	X	X			X		X
Urine Pregnancy Test		X			X		X
WOMAC	X	X	X	X	X	X	X
KOOS QOL		X	X	X	X	X	X
GPAQ, Index knee aspiration and collection of synovial fluid		X			X		
Measured Function Device	-----X-----						
1 st treatment administration		X					
Evaluation for repeat administration, 2 nd (repeat) treatment administration					X		
AEs & ConMeds		-----X-----					

## 2.5. Study Variables

### 2.5.1. Safety Variables

Safety and tolerability will be evaluated on the basis of findings from the following assessments:

- Adverse events
- Physical examinations
- Index knee assessments
- Vital signs
- Clinical laboratory evaluations
- Index knee X-ray

### 2.5.2. Exploratory Efficacy Variables

The following exploratory efficacy endpoints will be analyzed as described in the SAP:

- Western Ontario and McMaster Universities (WOMAC®) A (pain subscale), B (stiffness subscale), C (function subscale), and total score at all time points.

- Knee injury and Osteoarthritis Outcome Score (KOOS) Quality of Life (QOL) Subscale at all time points.
- Daily activity measured as steps per day from Day 1 to Week 12.
- Global Physical Activity Questionnaire (GPAQ) domains (activity at work, travel to and from places and recreational activities) and total score at baseline/Day 1 and Week 12.

### **3. PATIENT POPULATIONS**

#### **3.1. Population Definitions**

The following patient populations will be evaluated and used for presentation and analysis of data at the conclusion of the study:

##### **Safety Population (SP):**

The Safety Population (SP) will include all patients who receive study treatment. The Safety Population will be used to assess safety and tolerability endpoints.

##### **Full Analysis Set (FAS):**

The Full Analysis Set (FAS) population will include all patients who receive study treatment and provide at least one post-baseline efficacy endpoint assessment. The FAS population will be used to examine exploratory efficacy endpoints.

##### **Biomarker Population (BP)**

The Biomarker Population (BP) will include all patients who receive study treatment and provide at least one synovial fluid sample for biomarker analysis. The BP will be used for future biomarker analyses.

##### **Per Protocol Imaging Population (PPIP)**

The Per Protocol Imaging Population (PPIP) will include all patients in the SP who have quantifiable x-ray imaging values at baseline and Week 52/End of Study except those patients who are terminated early or have major protocol deviations that could affect image results. These major protocol deviations will be identified by Flexion medical without regard to individual patient imaging data.

Additional study populations may be defined to meet interim analysis requirements. These population definitions will be fully specified and documented in an interim SAP (iSAP) and in the final CSR.

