#### **7.4.4. Removal of Patients from Therapy or Assessments**

Each patient will be informed of his/her right to discontinue from the study at any time for any reason and without prejudice to alternative treatment. The Principal Investigator may also discontinue a patient from the study at any time if, for example, he/she considers the patient's health to be compromised by remaining in the study, or the study is prematurely terminated. In these cases the Principal Investigator will:

1. attempt to complete the study assessments defined for the Early Termination Visit\*
2. determine whether the patient is willing to be contacted to follow ongoing or new AEs through Week 12 for patients who only receive a single injection, or through Week 52 for patients who receive a second injection (if reason for discontinuation is not "withdrew consent") and contact patient as necessary (via phone or in-person). Concomitant medications associated with any AE will also be captured.
3. document patient consent in the source document for continued follow-up

*\*Note: Early Termination visits should follow the Week 52 visit schedule*

Data collected from discontinued patients will be included in the clinical study report. Patients who discontinue from the study may be replaced at the discretion of the Sponsor.

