### 8.1. Adverse Events

#### 8.1.1. Definitions

An AE is any untoward medical occurrence in a patient or clinical investigation patient administered a pharmaceutical product and that does not necessarily have a causal relationship with this treatment.

An AE can therefore be:

- Any unfavorable and unintended sign (including an abnormal laboratory finding), symptom, or disease temporally associated with the use of a medicinal (investigational) product, whether or not related to the medicinal (investigational) product.
- Any clinically significant abnormality found on an ECG, laboratory test or physical examination.
- Any worsening (i.e., any clinical significant adverse change in frequency and/or intensity) of a preexisting condition, which is temporally associated with the use of the medicinal (investigational) product, is also an AE.

An SAE is any untoward medical occurrence that at any dose:

- Results in death,
  - This serious criterion applies if the patient's death is a direct outcome of a reported AE.
- Is life-threatening,
  - This serious criterion refers to an event in which the patient was at substantial risk of death at the time of the event; it does not refer to an event which hypothetically might have caused death if it were more severe.
- Requires inpatient hospitalization or prolongation of existing hospitalization,
  - This serious criterion applies if the reported AE requires at least a 24-hour inpatient hospitalization or, if in the opinion of the Principal Investigator, prolongs an existing hospitalization. A hospitalization for an elective procedure or a routinely scheduled treatment is not an SAE by this criterion because a "procedure" or a "treatment" is not an untoward medical occurrence.

- Results in permanent or significant disability/incapacity, or
  - This serious criterion applies if the “disability” caused by the reported AE results in a substantial disruption of the patient’s ability to carry out normal life functions.
- Is a congenital anomaly/birth defect.
  - This serious criterion applies if a patient exposed to a medicinal (investigational) product gives birth to a child with congenital anomaly or birth defect.

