## Osteonecrosis and Insufficiency Fracture

Osteonecrosis and insufficiency fracture are each measured on a binary scale as absent or present (0=absent, 1=present) and will be adjudicated as follows:

- If Reader 1 and Reader 2 agree (are concordant) on the score of absent or present, then that score is used in the analysis.
- If Reader 1 and Reader 2 do not agree (are discordant) on the score of absent or present, then the X-ray will be read by a third independent radiologist and scored as absent or present. The adjudicated score will agree with either Reader 1 or Reader 2 and that score will be used in the analysis.

Change from baseline to end of study in JSON score will be presented for two-dose patients by patient group (timing of second dose) and for all two-dose patients combined. Any patients whose serial x-rays demonstrate a  $\geq 2$ -point grade increase in JSON will be categorized as indicating Chondrolysis. The frequency and percentage of Chondrolysis will be presented in a summary table for the PPIP and SP separately.

Shift tables of joint space narrowing, subchondral bone changes, osteonecrosis and insufficiency fracture will be presented for two-dose patients, showing shifts from baseline to the end of study by patient group (timing of second dose) and for all two-dose patients combined. These tables will be presented for the PPIP and SP separately.

These X-ray data for all patients, including results for each reader, will be presented in a by patient listing. A separate listing will present baseline Kellgren-Lawrence (K-L) Grade.

After review of X-ray results additional sensitivity analyses may be performed to better understand imaging results.

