#### **4.10.7. Surgical Procedures**

Surgical procedures that occurred during the study will be provided in a data listing.

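### The structural X-ray rates count only two-dose patients with a readable end film of the native index knee; replaced or unfilmed knees have no end value, and index-knee surgery is only listed

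*SAP*

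**What the plan says.** **Imaging populations.** SAP 3.1 builds the PPIP from SP patients with quantifiable films at baseline and Week 52/End of Study, "except those patients who are terminated early or have major protocol deviations that could affect image results". For the SP, "The Safety Population (SP) will include all patients who receive study treatment".

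**Tables.** SAP 4.10.5 reports both sets. For chondrolysis, "The frequency and percentage of Chondrolysis will be presented in a summary table for the PPIP and SP separately". For the shift tables of joint space narrowing (JSN), subchondral bone changes, osteonecrosis and insufficiency fracture, "These tables will be presented for the PPIP and SP separately".

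**Films.** Under Protocol Table 1 and 7.9.4, only two-dose patients have an end-of-study X-ray, and the films named for central reading are those at Screening and Week 52. For patients who leave, Protocol 7.4.4 asks the investigator to "attempt to complete the study assessments defined for the Early Termination Visit" and notes that "Early Termination visits should follow the Week 52 visit schedule".

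**Missing data.** SAP 4.2.8 imputes nothing outside WOMAC and KOOS QOL. SAP 4.2.1 gives categorical tables a missing category as a general rule.

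**Surgery.** SAP 4.10.7 says: "Surgical procedures that occurred during the study will be provided in a data listing". Protocol 8.1.1 adds, under the hospitalization criterion: "A hospitalization for an elective procedure or a routinely scheduled treatment is not an SAE by this criterion".

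**The concern.** Safety of repeat dosing is the primary objective, and Protocol 7.7.1 makes the index-knee X-ray a safety variable. Protocol 5.1 describes osteoarthritis as ending, for many patients, in joint replacement. Kellgren-Lawrence grade 4 knees are eligible, while planned or anticipated index-knee surgery is an exclusion (Protocol 7.4.2.2, criterion 13). An index-knee arthroplasty during the 52 weeks would therefore be one that was not foreseen at entry, and a reader would expect to find it beside the structural results.

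The plan does not put it there. A replaced knee has no native joint to score, and SAP 4.10.5 gives no rule for it. A patient who leaves without a film is in the same position. If such knees differ from those that were filmed, a rate computed on filmed knees does not describe all knees that received two injections.

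**Working it through.** **1. Who can contribute an end value**

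| Two-dose patient | PPIP | SP |
|---|---|---|
| Completes, readable Week 52 film, no relevant major deviation | counts | counts |
| Leaves early, readable film at the termination visit | excluded by rule | can count, if the film is centrally read |
| Leaves early, no film | no end value | no end value |
| Index knee replaced before the end film | no native end value | no native end value |

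The PPIP already requires both films, so its early-termination exception acts only on the second row. The gap common to both populations is the last two rows.

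**2. Planning figure** (Protocol 9.3, SAP 4.1: about 200 enrolled, 66% given a second dose, 75% of those completing)

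- Two-dose patients: 200 × 0.66 = 132.
- Two-dose completers: 132 × 0.75 = 99, against the stated 100. Inversely, 100 / (0.66 × 0.75) = 202.02, against the stated 200. The plan's figure reproduces.
- Two-dose non-completers: 132 − 99 = 33, or 25%.

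SAP section 5 reports that more than 90% received a second dose, with about 10 single-dose patients. Assuming 190 two-dose patients and the same 75%, 142 complete and 48 do not (190 × 0.75 = 142.5).

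**3. How wide the unobserved part could be**

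This illustrates bounds and is not an estimate. Assume 5% JSN worsening in filmed knees, borrowed from 7/140 in the 24-week single-dose study FX006-2014-008 (Protocol 5.2.8). Completers then give 5/99 = 5.1%. The share of the 33 non-completers with a termination film is not in the documents, so it runs from 0 to 100%. The lower bound counts no unread knee as worsened, and the upper bound counts every one.

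| Share filmed | Knees unread | Lower bound | Upper bound |
|---|---|---|---|
| 0% | 33 | 5/132 = 3.8% | 38/132 = 28.8% |
| 25% | 25 | 5/132 = 3.8% | 30/132 = 22.7% |
| 50% | 17 | 6/132 = 4.5% | 23/132 = 17.4% |
| 75% | 8 | 6/132 = 4.5% | 14/132 = 10.6% |
| 100% | 0 | 7/132 = 5.3% | 7/132 = 5.3% |

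The first row shows why the denominator must be stated. The same five events are 5.1% of filmed knees but 3.8% of all two-dose patients if unread knees stay in the denominator.

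With 190 two-dose patients and no termination films, the completer rate is 7/142 = 4.9% and the upper bound is (7 + 48)/190 = 28.9%.

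**4. Evidence on direction**

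In that same study, JSN worsened in 7 + 6 + 5 = 18 of 140 + 148 + 145 = 433 patients with both scheduled films, which is 4.2% (95% CI 2.5% to 6.5%). Among early terminators with a final film it worsened in 2/18, or 11.1% (1.4% to 34.7%). Fisher's exact test gives p = 0.19. Of those two, one had FX006 and one had placebo.

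If 11.1% applied to all 33 non-completers, about 4 would worsen, giving (5 + 4)/132 = 6.8% against 5.1% in completers.

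**5. Arthroplasty**

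No count is given. If no chondrolysis were seen in 99 completers (0/99, upper 95% limit 3.7%), a rate that also counted 2 or 5 arthroplasties would be 2/132 = 1.5% (0.2% to 5.4%) or 5/132 = 3.8% (1.2% to 8.6%). The 2 and the 5 are assumptions.

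**The case against.** A reader might infer from the PPIP definition that early terminators drop out of the structural safety rates altogether. They do not. Every structural table is also run on the SP, and the termination visit follows the Week 52 schedule, which includes an X-ray for two-dose patients. Restricting a per-protocol imaging set to completers is defensible, because it keeps follow-up time uniform.

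A reader might also infer that harm leading to surgery is hidden. The documents do not support that either. The elective-admission exemption applies to one seriousness criterion only. Clinically significant worsening of a pre-existing condition is an AE (Protocol 8.1.1), a change in the index knee from baseline is to be reported as an AE (8.1.5), and the disability and important-medical-event provisions still apply. Deterioration can therefore reach the index-knee AE, SAE and discontinuation tables in SAP 4.10.1. SAP 4.5 tabulates reasons for early termination and lists reasons for PPIP exclusion. The table shells are a separate document not available here and may set the SP denominator.

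All of this stands, and it limits the point. It does not remove it. AE and disposition tables never enter the structural rates. A missing category, if used, would not separate a replaced knee from a missed visit. The termination visit is only attempted, and central reading of its film is inferred rather than stated. SAP 4.10.5 allows further imaging sensitivity analyses, but only as an option after the X-ray results have been reviewed.

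**Conclusion.** The point holds in a limited form. Followed exactly, the plan gives structural rates conditional on a surviving, imaged native knee. In the SP the gap is confined to two-dose patients whose index knee was replaced or who have no readable end film.

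It is tempting to conclude that the plan understates structural harm by some multiple. The documents do not support that. They give no number of arthroplasties and no rate of termination films. The one internal comparison (2/18 against 18/433) points towards more worsening in early leavers but is inconclusive. Nor can an arthroplasty be equated with a missed chondrolysis: that endpoint needs a rise of at least 2 on a 0 to 3 JSN scale, so a knee at baseline 2 or 3 could never meet it.

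What can be sized is the number at risk of being unobserved: up to about 33 of 132 on the planning rates, or 48 of an assumed 190. The percentages in the working rest on a 5% rate borrowed from a shorter single-dose study and show bounds only.

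**What to change.** 1. **SAP 4.10.7.** Tabulate index-knee arthroplasty and other structural index-knee surgery for two-dose patients: n, % and time since last dose. Keep the listing.
2. **SAP 4.10.5.** Name the SP as the main population for structural safety, with all two-dose patients as the denominator. Add separate rows for no end film and for index-knee arthroplasty before the end film. Add a sensitivity rate that counts arthroplasty as a structural event, with each component shown separately.
3. **SAP 4.10.5, with Protocol 7.9.4 and Table 1 in agreement.** State that early-termination films are centrally read and enter the SP tables.

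The PPIP may stay restricted to completers as a supportive set.

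The cost is SAP wording and a few table rows, from data the study already collects, plus central reading of termination films if that is not already arranged. The downside is that surgery also reflects severe osteoarthritis at entry and patient choice. It should therefore stand as its own component and not be merged into the chondrolysis rate.
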